2.0 OBJECTIVES

Primary objectives:

1. To assess the safety of COVID-19 vaccines in pregnant and lactating individuals

2. To describe the effectiveness of COVID-19 vaccines in pregnant and lactating individuals

3. To examine attitudes towards COVID-19 vaccination, and other vaccinations, including RSV, among pregnant and lactating individuals

4. To examine the immunogenicity of COVID-19 vaccines within a subset of pregnant individuals and for their infants

5. To assess attitudes and the impact of co-administration of the COVID-19 vaccine with other regular vaccinations, such as the influenza vaccine, among pregnant and lactating individuals

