4.2 Data Collection

Once consent has been obtained, the baseline survey will automatically be pushed to the participant. The baseline answers will determine if pregnancy and or vaccine outcome surveys are to be answered at the same time. A short follow-up questionnaire will be administered on December 1st 2023 and another on February 1st 2024 to capture changes in vaccination status, COVID-19 status, pregnancy outcomes or significant health events. The follow-up surveys will determine if/when outcome surveys need to be completed. If consent is withdrawn, the study will immediately cease for the participant. The survey modules are as follows:

1. Baseline survey: Pregnancy status, vaccination status, demographics, health history, COVID-19 history & pregnancy history - Administered at enrollment starting Sept 1, 2023 until Jan 31, 2024

2. Pregnancy Outcomes: Pregnancy & infant outcomes – Administered if pregnancy started in 2023 and are not currently pregnant

3. Vaccine Outcomes: Answered if a dose of a COVID-19 vaccine received during the current pregnancy

4. Vaccine Attitudes 1: Feelings, opinions & attitudes towards vaccines– Administered at end of surveys received at baseline

5. Vaccine Attitudes 2: Feelings, opinions, and attitudes towards the Respiratory syncytial virus (RSV) – Administered following the completion of Vaccine Attitudes 1

6. Follow-up survey: 2 time-based follow-up surveys administered on December 1st, 2023, and on February 1st, 2024 with reminders sent out periodically throughout study duration
7. Health Event: Significant health events resulting in a visit to the emergency department or hospitalization – Administered if triggered by Follow-up survey

In the event of an adverse reaction or major health event, the study team will contact a participant for further health information.

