Data collected from individuals who do not receive COVID-19 vaccines will act as an internal comparison group. We will also capture self-identified gender through our online demographics questionnaire and examine differences by gender. The module on COVID-19 vaccination history will include type of vaccine received, number of doses and dosing interval. Vaccine safety endpoints will be coordinated with the Canadian National Vaccine Safety Network (CANVAS) endpoints: adverse events as detailed in data collection forms, severity and duration of adverse event, resultant medical visits (including to emergency department) or hospitalization, and treatments administered.

Pregnancy and infant safety outcomes measured are key outcomes identified by the Pan-Canadian, surveillance CANCOVID-Preg team. These major pregnancy complications/outcomes include but are not limited to gestational hypertension, gestational diabetes, placental abruption, infant birthweight, preterm birth, NICU admission, congenital anomalies, spontaneous abortion or termination, and stillbirth or neonatal death. Postnatally, including infants of women vaccinated during lactation, infant SARS-CoV-2 infection, hospitalization, growth parameters, and neurodevelopment (hyper vigilance) will be ascertained.

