4.5 Statistical Analysis and Metrics

To adequately power for comparisons of adverse events, we used estimates of vaccine-related adverse events (i.e. pain at injection site, redness, swelling, fever, fatigue, chills, headache, muscle pain, joint pain, grade 4 serious adverse events) from the subset of younger participants in the Pfizer vaccine trial, as an example (12). The rate of overall adverse events was 25%, and with a sample size of 451 in the vaccinated cohort we could estimate this prevalence with $\pm 4\%$ precision and 95% confidence. Sample sizes are highly feasible and will allow for comparison of adverse obstetrical and infant outcomes between vaccinated and unvaccinated participants. Given a sample size of 500 per group (vaccinated vs. unvaccinated) we would have 80% power to detect a minimum relative risk of 1.5.

The immunogenicity sub-study would require 89 participants, assuming 10% loss to follow up to estimate a 70% seroconversion rate with \pm 10% precision and 95% confidence. A seroconversion rate closer to 80% would require 68 participants. For comparisons of antibody levels, using estimates for the 18-55y age group (13) we would need approximately 48 participants to demonstrate a 10% difference in geometric mean titer with 95% power and assuming an attrition rate of 10% per visit.

The presence of any adverse outcomes (vaccine and pregnancy-related) will be compared between vaccinated and unvaccinated using time-varying Cox's proportional hazards models (14), stratified by vaccine type, and including important confounders. Effectiveness will be assessed descriptively through participant reporting of positive SARS-CoV-2 tests and COVID-19 diagnoses in vaccinated

and unvaccinated participants. Clinical features of breakthrough cases will be described in those vaccinated. Exploratory analyses will investigate differences between vaccinated and unvaccinated people. Clinical severity will be compared with unvaccinated people in the CANCOVID-Preg cohort. This will include tracking of infections with variants of concern where possible in both vaccinated and unvaccinated participants.

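### Effectiveness is compared by vaccination status without using the COVID-19 history collected at baseline, so unequal earlier infection could make the vaccine look less or more effective than it is

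*Protocol*

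**What the plan says.** Protocol section 2.0 lists five primary objectives. The second is "To describe the effectiveness of COVID-19 vaccines in pregnant and lactating individuals".

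The only method given for it is in section 4.5: "Effectiveness will be assessed descriptively through participant reporting of positive SARS-CoV-2 tests and COVID-19 diagnoses in vaccinated" and unvaccinated participants. Section 4.5 adds a description of breakthrough cases, a comparison of clinical severity with an outside cohort, and the general statement "Exploratory analyses will investigate differences between vaccinated and unvaccinated people".

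The comparison group is not randomised. Section 4.2 states: "Data collected from individuals who do not receive COVID-19 vaccines will act as an internal comparison group". Section 3.2 sets only an age limit and a pregnancy that began in 2023, so people who have already had COVID-19 can enrol.

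The relevant covariate is collected. Section 4.2 lists the content of the baseline survey as "Pregnancy status, vaccination status, demographics, health history, COVID-19 history & pregnancy history". Two follow-up surveys, on 1 December 2023 and 1 February 2024, are meant "to capture changes in vaccination status, COVID-19 status, pregnancy outcomes or significant health events".

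Confounders are mentioned once in section 4.5, for the Cox models of adverse outcomes: "stratified by vaccine type, and including important confounders". Nothing equivalent is attached to effectiveness.

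**The concern.** An earlier infection plausibly lowers the chance of another. People who take a vaccine and people who do not may differ in how often they have already had COVID-19. If they do, a table of infections by vaccination status alone carries two effects, and the reader cannot separate them.

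The distortion can go either way. If earlier infection is commoner in the unvaccinated, their infection count is held down and the vaccine looks weaker than it is. If it is commoner in the vaccinated, the vaccine looks stronger.

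This matters because the results are meant for use. Section 3.1 says the data will guide recommendations by national and provincial advisory bodies, and section 4.7 promises monthly reports that are also made public. A crude table under the label of effectiveness could therefore reach decision-makers before any refined analysis.

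**Working it through.** **No figure to reproduce.** The Protocol gives no effectiveness estimate, no infection risk and no prior-infection share. Its figure of 500 per group and a relative risk of 1.5 is for obstetrical and infant outcomes. What follows therefore sizes a possible bias and corrects no stated number.

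**Model.** Let VE be the true protection, the same with and without earlier infection. Let r be the reduction in risk from earlier infection, and pv and pu the shares with earlier infection among vaccinated and unvaccinated. Then

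crude RR = (1 − VE) × (1 − r·pv) / (1 − r·pu), and apparent protection = 1 − crude RR.

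All four inputs are assumptions.

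**Results with VE = 40% (true RR 0.60).**

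| r | pu | pv | Calculation | Crude RR | Protection reads |
|---|---|---|---|---|---|
| any | equal to pv | equal to pu | 0.6 × 1 | 0.600 | 40% |
| 0.3 | 0.7 | 0.6 | 0.6 × 0.82/0.79 | 0.623 | 38% |
| 0.5 | 0.8 | 0.6 | 0.6 × 0.70/0.60 | 0.700 | 30% |
| 0.7 | 0.8 | 0.6 | 0.6 × 0.58/0.44 | 0.791 | 21% |
| 0.7 | 0.9 | 0.6 | 0.6 × 0.58/0.37 | 0.941 | 6% |
| 0.5 | 0.6 | 0.7 | 0.6 × 0.65/0.70 | 0.557 | 44% |
| 0.7 | 0.6 | 0.7 | 0.6 × 0.51/0.58 | 0.528 | 47% |
| 0.7 | 0.6 | 0.8 | 0.6 × 0.44/0.58 | 0.455 | 54% |

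**A wider, symmetric imbalance (30% against 70%).**

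- VE 50%, pv = 0.3, pu = 0.7: r = 0.5 gives 0.5 × 0.85/0.65 = 0.654, which reads 35%. r = 0.8 gives 0.5 × 0.76/0.44 = 0.864, which reads 14%.
- VE 50%, reversed: r = 0.5 gives 0.5 × 0.65/0.85 = 0.382, which reads 62%. r = 0.8 gives 0.5 × 0.44/0.76 = 0.289, which reads 71%.
- VE 30%, pv = 0.3, pu = 0.7: r = 0.5 gives 0.7 × 0.85/0.65 = 0.915, which reads 8%. r = 0.8 gives 0.7 × 0.76/0.44 = 1.209, an apparent harm of 21%.

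**What stratifying does in this model.** Take 500 per group, r = 0.7, pu = 0.8, pv = 0.6 and VE = 40%. Let b be the risk in unvaccinated people without earlier infection; it cancels.

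- No earlier infection: 200 vaccinated with 200 × 0.6b = 120b cases; 100 unvaccinated with 100b cases.
- Earlier infection: 300 vaccinated with 300 × 0.3 × 0.6b = 54b cases; 400 unvaccinated with 400 × 0.3b = 120b cases.
- Crude RR: (174b/500) / (220b/500) = 0.791.
- Mantel-Haenszel RR: (120·100/300 + 54·400/700) / (100·200/300 + 120·300/700) = 70.86/118.10 = 0.600.

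The assumed effect is recovered, provided that history is reported correctly and was not itself affected by the vaccine.

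**The second proviso matters here.** Enrolment runs from 1 September 2023 to 31 January 2024, and a dose may come well before it. COVID-19 after the dose but before enrolment is a breakthrough case. Filing it as prior history would condition on something the vaccine may have changed, and would remove an outcome from the count. The dividing line therefore has to be the dose, not enrolment.

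**The case against.** The strongest reply has four parts.

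1. **Silence is not a decision.** Section 4.5 does not say that COVID-19 history will be ignored. Choosing the stratifiers of a descriptive table is often left to the statistical analysis plan, which is not shown, and the unspecified exploratory analyses could include it. This stands in part: a reader might infer that the Protocol rules out any use of prior infection, and it does not. But the Protocol names covariates or confounders for safety, attitudes and the immune sub-study, and gives effectiveness a bare two-group split. Followed as written, the plan yields the confounded contrast.

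2. **The objective is descriptive.** No vaccine-effectiveness percentage, test or causal claim is promised. This stands, so the fault lies in how the contrast will be read and not in a wrong number. It does not remove the point, since a stratified table is equally descriptive.

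3. **The size is all assumption.** This stands. A reader might infer that earlier infection will hide the vaccine's effect. The documents do not support that: they say nothing on which group had more earlier infection, the mildest case above moves 40% only to 38%, and the reverse imbalance inflates the effect.

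4. **The obvious remedy has its own faults.** Splitting by COVID-19 before enrolment would treat some breakthrough cases as history. Counting only infections after enrolment would discard those reported at baseline, and someone enrolled on 31 January 2024 gets the last scheduled survey the next day. A rate ratio needs dates that the Protocol does not show are collected. All of this stands and shapes the fix.

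**Conclusion.** The point holds in a limited form. Section 4.5 describes effectiveness by vaccination status alone and leaves unused a baseline variable that bears directly on susceptibility. A difference in earlier infection between these self-selected groups could move the apparent effect in either direction.

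The figures above show what is possible, not what will occur. They rest on assumed protection from vaccine and infection, assumed prior-infection shares, and equal vaccine protection in both strata. With equal shares the bias vanishes in this model.

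It is worth correcting because the results are meant to inform recommendations and the correction is small. It does not show a contradiction or a miscalculation in the Protocol.

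**What to change.** Add to section 4.5:

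- Tabulate reported infections by vaccination status separately for participants with and without reported COVID-19 before the vaccine dose being evaluated. State which dose that is.
- For the unvaccinated, define history as COVID-19 before a comparable index date, such as enrolment. State the rule so that both groups are counted over comparable periods.
- Count infections after vaccination as outcomes, never as prior history, including those that precede enrolment.
- Show the crude table alongside.
- Give a Mantel-Haenszel summary ratio across the two strata with a 95% CI: a risk ratio, or a rate ratio only if infection and vaccination dates allow person-time.
- Note that history is self-reported, so unrecognised infections leave residual confounding.

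**Cost.** A few sentences and one further table split. The strata are smaller and their intervals wider: in the worked example above, only 100 of 500 unvaccinated participants have no earlier infection. COVID-19 history is already collected, but section 4.2 does not say whether the forms place each infection before or after the dose. That must be checked; if they do not, a date or order question is needed, and participants whose order is unknown should be shown as a separate category.

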4.7 Knowledge Translation

Analysis and reporting from this project will be ongoing, as data become available. We will produce regular monthly national reports for distribution to our national and provincial public health partners and through the additional networks of the CANCOVID-Preg members. These reports will also be publicly shared, including with study participants, via our website, social media channels, and traditional media outlets. A knowledge broker will be engaged as part of the team to optimize translation of our findings to public health officials and a diverse range of the Canadian population, and to enhance translation of these findings into clinical guidance and public knowledge. In addition, we will leverage our partnerships with pan-Canadian university communications departments to expand the reach of our recruitment and knowledge translation outputs. Finally, our team includes clinician and policy knowledge users who will be active in the interpretation and dissemination of results, including amongst professional organizations that influence vaccine recommendations (e.g. SOGC).

REFERENCES

- 1. World Health Organization. Weekly Operational Update on Covid-19 -19 April 2021 (Accessed April 20, 2021). https://www.who.int/publications/m/item/weekly-operational-update-on-covid-19---19-april-2021.
- Government of Canada. Coronavirus diseases (SARS-COV-2): Outbreak Update. (Accessed April 20, 2020). https://www.canada.ca/en/public-health/services/diseases/2019-novel-coronavirus-infection.html#a1.
- Canadian Surveillance of COVID-19 in Pregnancy: Epidemiology M, and Infant Outcomes. Report #3: Maternal and Infant Outcomes (March 1, 2020 to December 31, 2020) from Five Canadian Provinces. 2021.

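### The severity comparison with unvaccinated CANCOVID-Preg cases is not restricted by calendar period, variant or severity definition, so era and ascertainment are mixed with vaccination status

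*Protocol*

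**What the plan says.** Effectiveness is the second of five primary objectives and is worded as description: "To describe the effectiveness of COVID-19 vaccines in pregnant and lactating individuals" (Protocol, section 2.0).

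Section 4.5 handles three kinds of outcome differently:

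- **Adverse outcomes:** "The presence of any adverse outcomes (vaccine and pregnancy-related) will be compared between vaccinated and unvaccinated using time-varying Cox's proportional hazards models", stratified by vaccine type and with confounders included.
- **Infection:** "Effectiveness will be assessed descriptively through participant reporting of positive SARS-CoV-2 tests" and diagnoses, in vaccinated and unvaccinated participants. Breakthrough cases are described, and unspecified exploratory analyses look at differences by vaccination status.
- **Severity:** "Clinical severity will be compared with unvaccinated people in the CANCOVID-Preg cohort". The next sentence adds: "This will include tracking of infections with variants of concern where possible in both vaccinated and unvaccinated participants".

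The registry also has its own concurrent controls: "Data collected from individuals who do not receive COVID-19 vaccines will act as an internal comparison group" (section 4.2).

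On timing, participants must have become pregnant in 2023 (section 3.2). Baseline surveys run from 1 September 2023 to 31 January 2024, and follow-up surveys go out on 1 December 2023 and 1 February 2024 (section 4.2). The only dated CANCOVID-Preg output is entry 5 of the reference list: "Report #3: Maternal and Infant Outcomes (March 1, 2020 to December 31, 2020".

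**The concern.** The severity sentence chooses a comparator. It takes unvaccinated cases from another data source and places no condition on when they occurred, which variant caused them or how severity was graded. Section 1.2 says that provinces widened the vaccine offer to all pregnant people on the strength of CANCOVID-Preg data, so that cohort must contain cases from before the wider offer. An unrestricted unvaccinated stratum would include them.

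The two sources also find cases differently. Section 4.2 describes CANCOVID-Preg as pan-Canadian surveillance, while the registry relies on volunteers answering web surveys (sections 3.1 and 4.1). A difference in severity could therefore reflect period, variant, case-finding or vaccination, and the comparison as written cannot separate them. Results are meant to inform national and provincial vaccine advisory bodies (section 3.1) and to appear in monthly public reports (section 4.7), so a misread contrast would travel quickly.

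A smaller issue concerns infection reports. Surveys fall on fixed calendar dates and vaccination status can change during the study. Simple proportions by status would then mix unequal observation times.

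**Working it through.** The protocol gives no effect size, sample size or precision for effectiveness or severity, so there is no stated figure to reproduce. The check sets the dates side by side and then shows what the comparison would return under no vaccine effect. All severity ratios, shares and infection rates below are assumptions.

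**1. Periods.**

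| | Registry | CANCOVID-Preg |
|---|---|---|
| Period in the protocol | Pregnancies from 2023; surveys issued 1 Sept 2023 to 1 Feb 2024 | One report, March to December 2020; full period not stated |
| Case-finding | Volunteer self-report | Surveillance |
| Severity definition for the comparison | Not stated | Not stated |

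At least part of the external cohort predates the registry by about three years. How much overlaps is not known.

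**2. Severity with a vaccine of no effect.** Let r be the risk of a severe outcome per case in the earlier period divided by that in the registry period. Let w be the share of external cases from the earlier period. Then

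apparent protection = 1 - 1/(w·r + 1 - w).

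- w = 0.25, r = 2: 1 - 1/1.25 = 20%
- w = 0.5, r = 3: 1 - 1/2 = 50%
- w = 1, r = 4: 1 - 1/4 = 75%
- w = 0 (all external cases from the registry period): 1 - 1/1 = 0%, whatever r is

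With w = 1 and r = k the formula becomes 1 - 1/k, the upper limit for a given ratio: 50%, 67% and 80% for k = 2, 3 and 5. If earlier cases were less likely to be severe (r below 1), the sign reverses. Differences in ascertainment would add to or subtract from these values and are not modelled.

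**3. Infection reports (secondary).** Prospective time from enrolment to issue of the last survey is 30 + 31 + 30 + 31 + 31 = 153 days for entry on 1 September, 31 + 31 = 62 days for entry on 1 December, and 1 day for entry on 31 January.

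Take the same assumed rate of 3% per month in both groups, with 2.5 months observed as vaccinated and 5 months as unvaccinated:

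- vaccinated: 1 - exp(-0.03 × 2.5) = 0.0723
- unvaccinated: 1 - exp(-0.03 × 5) = 0.1393
- ratio of proportions: 0.0723/0.1393 = 0.519, an apparent effectiveness of 48%

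If the observation times are swapped, the ratio is 0.1393/0.0723 = 1.93, an apparent harm. The rate ratio per person-month is 1.0 in both cases.

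**The case against.** The strongest reply is that effectiveness is expressly descriptive and that a statistical analysis plan, not shown here, may settle denominators, period restrictions and the handling of people whose status changes. Much of this stands for the infection reports. Section 4.5 does not prescribe crude proportions, so that part is a request for clarity and not an error. It stands less well for severity, where the protocol itself names the comparator and says that a comparison will be made.

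The neighbouring sentences help a little. Exploratory analyses by vaccination status are planned, and variants are tracked where possible. However, no use of the variant data in the severity comparison is stated, and tracking is not restriction or adjustment.

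The external cohort may also be a deliberate choice, because internal severe cases will be rare. Assume 500 unvaccinated participants (the group size used in section 4.5), 5% to 20% infected, and 1% to 5% of those severe. The expected count is then 500 × 0.05 × 0.01 = 0.25 to 500 × 0.20 × 0.05 = 5. This is a good reason to keep CANCOVID-Preg in view, but not to leave its period open.

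A reader might infer more than the documents support:

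- **That the comparator is wholly from 2020.** That period comes from one cited report. Overlap with 2023-24 is possible.
- **That infection effectiveness also rests on a historical control.** The external cohort is named for severity only; infections are described among registry participants.
- **That people are observed for only 1 to 153 days.** This is the prospective window to issue of the last survey. The baseline survey also takes COVID-19 history, reminders continue, and the timeline runs to March 2024.
- **That the bias favours vaccination.** Unequal observation matters only if it differs by vaccination status, and its direction depends on which group is observed longer. The protocol gives no basis for either.

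**Conclusion.** The point holds for the severity comparison. As written, it mixes vaccination status with calendar period, variant and ascertainment, because the external unvaccinated cases are unrestricted and at least some predate general vaccine access in pregnancy. The conclusion rests on sections 1.2, 3.2, 4.2 and 4.5 and needs no assumption about magnitude.

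The size cannot be derived from the documents. The limit of 1 - 1/k depends entirely on an assumed k, and the 20% to 75% results also need an assumed share of earlier cases. They show that the effect could be large, not that it is. The protocol makes no causal claim, so crediting the contrast to the vaccine is a risk of interpretation.

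The infection reports are a secondary point. Rates per person-time would be safer, but the direction and size of any distortion are unknown. The change is worth making before any severity comparison is reported.

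**What to change.** In section 4.5, or in the statistical analysis plan with a reference from it:

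1. Restrict the CANCOVID-Preg comparison to unvaccinated cases in calendar and variant periods that overlap the registry, using one severity definition for both sources. If this is not feasible, label the comparison as context that does not support a vaccine effect.
2. State the period that CANCOVID-Preg covers and how cases are ascertained in each source.
3. Report severity alongside the concurrent internal unvaccinated group of section 4.2.
4. Describe self-reported infections as rates per person-time with vaccination as a time-varying status, the approach that section 4.5 already takes for adverse outcomes. State how infections before enrolment, reported as COVID-19 history at baseline, enter the count.

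The cost is mainly wording. The statistical price is few severe cases, internal or overlapping, and so wide intervals and possibly no usable severity contrast. Dose and test dates must be obtainable. Section 4.2 lists vaccine type, number of doses and dosing interval but does not name test dates, so the survey forms need checking.
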